7.2.2.2. Criteria for Conditional Withholding of ABI-009 Due to Potential Hepatotoxicity

For patients who do not meet the criteria for permanent discontinuation of ABI-009 and have no underlying liver disease, and eligibility criteria requiring normal transaminases and TBL at baseline or patients with underlying liver disease and baseline abnormal transaminases, the following rules are recommended for withholding of ABI-009:

- Elevation of either AST or ALT according to the following schedule:

Baseline AST or ALT value	AST or ALT elevation
Any	> 8x ULN at any time
Any	> 5x ULN but < 8x ULN for ≥ 2 weeks
Any	> 5x ULN but < 8x ULN and unable to adhere to enhanced monitoring schedule
Any	≥ 3x ULN with clinical signs or symptoms that are consistent with hepatitis (such as right upper quadrant pain/tenderness, fever, nausea, vomiting, jaundice).

- OR: TBL > 3x ULN at any time
- OR: ALP > 8x ULN at any time

ABI-009 should be withheld pending investigation into alternative causes of DILI. Rechallenge may be considered if an alternative cause for impaired liver tests (ALT, AST, and ALP) and/or elevated TBL is discovered and the laboratory abnormalities resolve to normal or baseline.

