5. TABLE OF EVENTS

The schedule of assessments in [Table 2](#) outlines the specific time points for study assessments.

Table 2: Schedule of Assessments

Assessment ^a	Screening ^b (Day -14 to - 1)	Cycle 1 through Last Cycle (Treatment Period)		End of Treatment (EOT) Visit ^d	Follow-up Period ^e
		Day 1 ^c	Day 8		
General Assessments, Biomarkers, PK samples					
Informed Consent	X				
Demographics	X				
Medical History	X				
Physical Examination	X	X		X	
Vital Signs, Height and Weight	X	X ^f	X ^f	X ^f	
BSA Calculation		X ^m			
Prior/Concomitant Medication Evaluation ^g	X	X	X	Until 28 days after the last dose of IP	
Prior/Concurrent Procedures Evaluation ^g	X	X	X	Until 28 days after the last dose of IP	
ECOG PS	X	X		X	
Pregnancy Test ^h	X			X	
ECG (12 lead) ⁱ	X	X	X		
Survival status					X
Pre-treatment tissues (archival or fresh) (mandatory) ^j	X				
Tumor biopsy for Biomarkers ^k	X	Upon disease progression and/or end of last dose of IP			
Blood Sample for Biomarkers	X	Cycle 4/D1 and Upon disease progression and/or end of last dose of IP			
Blood Sample for Rapamycin (PK) ^l		Pre-treatment and at 0.5, 1, 2, 4 hrs post- treatment	Pre-treatment and at 0.5, 1, 2, 4 hrs post- treatment		
Adverse Events	Continuous starting from signing of Informed Consent until 28 days after last dose of IP				

Assessment ^a	Screening ^b (Day -14 to - 1)	Cycle 1 through Last Cycle (Treatment Period)		End of Treatment (EOT) Visit ^d	Follow-up Period ^e
		Day 1 ^c	Day 8		
ABI-009 Dosing		X	X		
Local Laboratory Assessments					
Clinical Chemistry Panel	X	X		X	
CBC, Differential, Platelet Count	X	X	X	X	
PT, PTT, INR	X				
Urinalysis	X				
Thyroid function	X	X			
HIV, HBV sAg, HBV cAb, HCV Ab	X				
Fasting Lipids	X	X ⁿ			
Imaging and Efficacy Assessments					
CT/MR ^o	X	Every 6 weeks after C1 D1 for the first year, then every 12 weeks thereafter		X	

- a. Unless otherwise specified, visits must occur within \pm 2 days of the planned visit date.
- b. Screening evaluations to be obtained \leq 14 days prior to enrollment unless specified otherwise.
- c. Day 1 evaluations can be omitted if screening evaluations are performed within 72 hours of Cycle 1 Day 1.
- d. End of Treatment Visit must occur at least 4 weeks (\pm 7 days) after the last dose of ABI-009.

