6.2.1. Day 1 Assessment

The following assessments will be performed on Day 1 of each cycle, unless otherwise specified:

- Physical examination
- Weight assessment
- BSA calculation (Calculated ONLY on C1/D1; to be recalculated only if the weight changes by > 10% in subsequent cycles)
- Concomitant medication and procedures evaluation
- Vital signs (temperature, systolic and diastolic blood pressure, and pulse)
- ECOG performance status

- ECG (12-lead ECG is to be conducted during infusion around the 30 min time point after start of infusion to coincide with the end of infusion period which lasts 30 minutes [+/- 10 min]). Day 1 ECG is conducted for every cycle.
- Clinical chemistry panel (including but not limited to sodium, potassium, chloride, glucose, alkaline phosphatase (ALP), AST/SGOT, ALT/SGPT, serum albumin)
- CBC, differential and platelet count
- Thyroid function
- Fasting lipids (every even numbered cycles starting with Cycle 2)
- Adverse Event assessment
- Pharmacokinetics assessment (only on Cycle 1 Day 1 at pre-treatment and at 0.5, 1, 2, 4 hrs post-treatment and Cycle 2 Day 1 at pre-treatment only)

Day 1 evaluations for Cycle 1 may be omitted if screening evaluations are performed within 72 hours of Cycle 1 Day 1. Laboratory assessments: chemistry, hematology, coagulation, urinalysis, pregnancy test (women of child-bearing potential, includes tubal ligation) (see [Table 3](#) for analyte listing).

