6.2.2. Day 8 Assessment

The following assessments will be performed on Day 8 of each cycle, unless otherwise specified:

- Concomitant medication and procedures evaluation
- Vital signs
- CBC, differential and platelet count
- Adverse Event assessment
- Pharmacokinetics assessment (only on Cycle 1 Day 8 pre-treatment and at 0.5, 1, 2, 4 hrs post-treatment)
- ECG (12-lead ECG is to be conducted during infusion around the 30 min time point after start of infusion to coincide with the end of infusion period which lasts 30 minutes [+/- 10 min]). Day 8 ECG is conducted only on Cycle 1.

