7.2.2.1. Criteria for Permanent Discontinuation of ABI-009 Due to Potential Hepatotoxicity

ABI-009 should be discontinued permanently and the patient should be followed for possible drug-induced liver injury (DILI), if **ALL** of the criteria below are met:

- TBL > 2x upper limit of normal (ULN) or INR > 1.5x
- AND increased AST or ALT from the relevant baseline value as specified below:

Baseline AST or ALT value	AST or ALT elevation
< ULN	≥ 3x ULN

- AND no other cause for the combination of the above laboratory abnormalities is immediately apparent; important alternative causes for elevated AST/ALT and/or TBL values include, but are not limited to:
 - Hepatobiliary tract disease
 - Viral hepatitis (eg, Hepatitis A/B/C/D/E, Epstein-Barr Virus, Cytomegalovirus, Herpes Simplex Virus, Varicella, Toxoplasmosis, and Parvovirus)
 - Right sided heart failure, hypotension or any cause of hypoxia to the liver causing ischemia.
 - Exposure to hepatotoxic agents/drugs or hepatotoxins, including herbal and dietary supplements, plants and mushrooms
 - Heritable disorders causing impaired glucuronidation (eg, Gilbert's Syndrome, Crigler-Najjar syndrome) and drugs that inhibit bilirubin glucuronidation (eg, indinavir, atazanavir)
 - Alpha-one antitrypsin deficiency
 - Alcoholic hepatitis
 - Autoimmune hepatitis
 - Wilson's disease and hemochromatosis
 - Nonalcoholic Fatty Liver Disease including Steatohepatitis (NASH)
 - Non-hepatic causes (eg, rhabdomylosis, hemolysis)

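### Low-cost safety improvement: without a Day 8 liver panel, a new asymptomatic rise after the Day 1 draw goes unseen by scheduled tests before the second infusion of each cycle

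*Combined protocol and SAP*

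**What the plan says.** **Holds and stops.** Section 7.2.2.2 introduces its criteria with "the following rules are recommended for withholding of ABI-009". For AST or ALT these include "> 8x ULN at any time" and "> 5x ULN but < 8x ULN for ≥ 2 weeks". Holds also apply at any time for TBL above 3x ULN or ALP above 8x ULN, and for AST or ALT of at least 3x ULN with symptoms of hepatitis. Section 7.2.2.1 stops drug permanently when "TBL > 2x upper limit of normal (ULN) or INR > 1.5x" occurs with a qualifying AST or ALT rise (at least 3x ULN from a baseline below ULN) and no other apparent cause.

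**Testing.** Section 6.2.1 lists for Day 1 of every cycle a "Clinical chemistry panel (including but not limited to sodium, potassium, chloride, glucose, alkaline phosphatase (ALP), AST/SGOT, ALT/SGPT, serum albumin"; Table 3 places TBL in the same panel. Section 6.2.2 opens with "The following assessments will be performed on Day 8 of each cycle, unless otherwise specified" and lists a CBC but no chemistry. Table 2 agrees: the chemistry row is marked at Screening, Day 1 and the End of Treatment Visit and is blank at Day 8, while the CBC row is marked in all four columns. Footnote c adds that "Day 1 evaluations can be omitted if screening evaluations are performed within 72 hours of Cycle 1 Day 1".

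**Dosing.** Section 7.1 gives drug weekly for two weeks of each 21-day cycle. Section 6.2 places dosing after the other pre-dose assessments of the visit.

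**The concern.** The liver holds are written as if a current result were at hand whenever drug is given, but the schedule supplies one at only every other infusion. At Day 8 the newest scheduled result is nominally 7 days old and was drawn before the latest dose. A site following the schedule exactly could therefore infuse a patient who is already above the plan's own 8x ULN hold, with nothing to show it if the patient has no symptoms.

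Cycle 1 is the clearest case. The Day 1 panel, if done, is drawn before any drug. The first scheduled liver test after exposure is then Cycle 2 Day 1, after two infusions.

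Blood counts do not have this gap, because the Day 8 CBC lets the hematologic hold in Table 5 operate mid-cycle. Table 5 has no hepatic row, so the liver-specific holds sit in section 7.2.2 alone. What is at stake is avoidable exposure in a small number of patients.

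**Working it through.** **1. The plan's own count.** From section 7.1: 24 weeks / 3 = 8 cycles; 8 x 2 = 16 infusions. The phase 1 schedule gives 24 / 4 = 6 cycles; 6 x 3 = 18. The reduction is 1 - 16/18 = 11.1%. The stated 16, 18 and 11% are all reproduced.

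**2. Infusions matched to tests.** Scheduled chemistry falls on study days 1, 22, 43 and so on. Infusions fall on days 1, 8, 22, 29, 43 and so on. Eight infusions have a same-day panel. The other eight (days 8, 29, 50, 71, 92, 113, 134, 155) do not.

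- Age of the latest scheduled result at Day 8: 8 - 1 = 7 days.
- In Cycle 1, if the Day 1 tests are omitted under footnote c: up to 7 + 3 = 10 days.
- Longest gap between scheduled tests: 21 days now, 14 with a Day 8 panel.

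**3. Infusions given under each schedule.** Each case is an asymptomatic rise that begins after the Day 1 draw.

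| Course of the rise | Current schedule | With Day 8 panel | Avoided |
|---|---|---|---|
| Above 8x ULN by Day 8 | Seen Day 22; Day 8 given | Seen and held Day 8 | 1 |
| Sustained 5-8x by Day 8, nominal timing | Seen Day 22, next scheduled test Day 43; Days 8, 22, 29 given | Seen Day 8, two weeks reached Day 22; Day 8 given | 2 |
| Same, Day 8 and Day 22 draws under 14 days apart | Days 8, 22, 29 given | Days 8, 22 given; held Day 29 | 1 |
| Same, but site holds at its discretion on Day 22 | Day 8 given | Day 8 given | 0 |
| Onset after the Day 8 draw | Seen Day 22 | Seen Day 22 | 0 |

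The third row arises because the nominal gap is exactly 22 - 8 = 14 days. With +/- 2 days at each visit it can be 10 to 18 days, so one visit shifted by a day can miss the two-week criterion on Day 22.

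**4. Patients likely to be affected.** Section 1.2.2.2 and Table 1 report grade 3 AST elevation in 2 of 26 phase 1 patients over all doses: 7.7%, exact 95% CI 0.9% to 25.1%. At 100 mg/m² there were no AST events of any grade in 7 patients (exact 95% upper limit 41%). Assume the pooled rate applies and that onset is uniform over the cycle, so that 7 of 21 days fall between the Day 1 and Day 8 draws:

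- 30 x 0.0769 x 7/21 = 0.77 patients
- over the CI: 30 x 0.0095 x 7/21 = 0.1 to 30 x 0.2513 x 7/21 = 2.5

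This is before requiring the rise to be asymptomatic and to reach the multiples in section 7.2.2.2. The documents give no ULN multiples for the phase 1 cases.

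**5. Cost.** One extra panel per cycle: 8 x 30 = 240 over 24 weeks if every patient stays on treatment.

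**The case against.** The best reply is that this is a design choice. Table 2 and sections 6.2.1 and 6.2.2 agree with one another, and nothing in the documents requires a liver test before each infusion. The holds act on any result, including an unscheduled one. Adverse events are assessed on Day 8, the symptom-triggered hold applies from 3x ULN, section 7.2.1 allows a discretionary hold and recommends withdrawal for toxicity unresolved at 14 days, and a DMC reviews safety early. The phase 1 rate pools doses up to 150 mg/m², with 9 of 26 patients above 100 mg/m². All of this stands and is why the priority is low. None of it, however, is a scheduled check for a silent rise before the Day 8 dose.

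Some stronger readings are tempting, but the documents do not support them:

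- *The liver rules cannot operate on Day 8.* They can: a Day 1 result that meets a hold carries forward.
- *Half of all infusions are at risk.* The 8 of 16 counts infusions without a same-day panel. Only a new rise in the preceding week matters.
- *Two full doses (200 mg/m²) would be saved per sustained 5-8x rise.* That is the nominal best case. Visit windows cut it to 1 and a discretionary hold to 0, and section 7.2.1 also provides for dose reduction.
- *Section 7.2.1 already expects chemistry on Day 8, because it makes the dose after a missed Day 8 depend on chemistries.* That dose is Day 1 of a new cycle, where the panel is already scheduled.
- *The missing interval in "> 5x ULN but < 8x ULN and unable to adhere to enhanced monitoring schedule" is the real defect.* Weekly tests starting when the rise is first seen on Day 22 reach two weeks on Day 36, after the Day 29 dose. Defining the interval would by itself avoid no infusion.

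**Conclusion.** The point holds as a cheap, low-priority safety improvement. The schedule leaves the Day 8 infusion without a same-day scheduled liver test in every cycle, and in Cycle 1 no scheduled test follows exposure until after two infusions. The gain from a Day 8 panel is one infusion for a new rise above 8x ULN present by Day 8, and 0 to 2 for a sustained 5-8x rise present by then. For onset later in the cycle there is no gain.

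The expected number of patients, about 0.8 of 30 (0.1 to 2.5), rests on the pooled phase 1 grade 3 AST rate carrying over to this dose and schedule and on uniform onset. It is likely to be high, because it does not yet require a silent rise at the stated multiples. The case therefore rests on the low cost of the change. A reader might infer some consequence for the efficacy result; the primary response-rate analysis is unaffected.

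**What to change.** Add AST, ALT, TBL and ALP to the Day 8 blood draw in Table 2 and section 6.2.2, with results reviewed before the Day 8 dose. Add INR as a reflex test when AST or ALT is at least 3x ULN, so that both arms of the permanent-stop rule in section 7.2.2.1 can be applied. Table 2 marks INR at screening only, although a general sentence in section 6.2.1 lists coagulation among the laboratory assessments. Leave all hold thresholds as written.

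In the document this is one mark in Table 2, one line in section 6.2.2 and a short reflex instruction. In conduct it is at most about 240 extra panels, on blood already being drawn for the CBC, plus an occasional INR. The real burden is that Day 8 dosing waits for a chemistry result. A few holds may also come earlier than they would now.

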7.2.2.3. Criteria for Rechallenge with ABI-009 After Potential Hepatotoxicity

The decision to rechallenge the patient should be discussed and agreed upon unanimously by the patient, investigator, and AADI medical monitor.

If signs or symptoms recur with rechallenge, then ABI-009 should be permanently discontinued. Patients who clearly meet the criteria for permanent discontinuation (as described in [Section 7.2.1](#)) should never be rechallenged.

7.2.3. Overdose

On a per dose basis, an overdose is defined as 10% over the protocol-specified dose of ABI-009 assigned to a given patient, regardless of any associated AEs or sequelae.

On a schedule or frequency basis, an overdose is defined as anything more frequent than the protocol required schedule or frequency.

On an infusion rate basis, an overdose is defined as any rate faster than the protocol-specified rate of 30 minutes for each infusion.

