- e. Follow-up for survival and initiation of anticancer therapy can be performed by telephone contact every 12 weeks (+/- 3 weeks) or more frequently if needed, from EOT Visit. All patients that discontinue study drug and have not withdrawn full consent to participate in the study will continue in the follow-up phase for survival and anticancer therapy. This evaluation may be made by record review and/or telephone contact.
- f. Vitals and weight only.
- g. Prior: record all medications taken and procedures done \leq 28 days prior to screening; Concomitant: any medications or procedures after the signing of informed consent.
- h. For females of childbearing potential only. A serum β -hCG pregnancy test must be performed to assess patient eligibility at screening prior to first IP administration (negative results required for IP administration). Urine pregnancy test will be performed at EOT Visit (can be done locally) and as clinically indicated as per institutional guidelines.
- i. ECG to be monitored at screening, Cycle 1 Day 1 and Day 8, and thereafter on Day 1 of every treatment Cycle. In each case ECG is to be monitored during infusion around the 30 min time point after start of infusion to coincide with the end of infusion period which lasts 30 minutes (+/- 10 min).
- j. Ensure the surgical pathology report is submitted with tumor tissue sample (either tumor block or unstained slides [min 6]).
- k. Biopsy tumor sample: formalin-fixed, paraffin-embedded (FFPE) tumor tissue or unstained slides from biopsy will be collected (tumor blocks are preferred – refer to Instruction Sheet for details). Screening tumor tissue (fresh/archival) required for biomarker analysis for all patients. On study tumor tissue collection is optional only for patients who provide additional consent.
- l. PK samples to be taken only at Cycle 1 on Day 1 and Day 8 (pre-treatment and at 0.5, 1, 2, and 4 hrs (+/- 10 min) post-treatment) and in Cycle 2 Day 1, when only a pre-treatment sample is required.
- m. Calculated ONLY on C1/D1; to be recalculated only if the weight changes by $>$ 10% in subsequent cycles.
- n. Every even numbered cycle starting with Cycle 2, eg C2, C4, C6, etc.

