7. DESCRIPTION OF STUDY TREATMENTS

7.1. ABI-009 Dosage, Administration, and Schedule

Treatment cycles are 21 days in duration and patients are treated until disease progression or unacceptable toxicities. Patients will receive ABI-009 100 mg/m² (IV infusion over 30 minutes, +/- 10 min) weekly for 2 weeks followed by a week of rest (2/3 weekly schedule). The schedule 2 weeks out of a 3 weekly schedule will allow the patient to have 1 week rest, when most of the toxicities occur, based on experience in the phase 1 study of ABI-009 (Protocol CA401) [38]. In terms of dose intensity within 6 months (24 weeks), the 2 out of 3 weekly schedule will consist of 16 administrations compared to 18 administrations with the prior 3 out of 4 weekly schedule. This reflects a global dose intensity reduction of 11% when comparing the 2 schedules. Two dose reduction levels are allowed: 75 mg/m² and 56 mg/m². A physician must be available at the time of administration of IP on dosing days that correspond to study visits. Supportive care per the institution's normal standard of care including concomitant medications can be provided at the investigator's discretion.

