6. Calculate the exact total dosing volume (to the nearest mL) of 5 mg/mL suspension required for the patient:

$$\text{Dosing volume (mL)} = \frac{\text{Total dose (mg)}}{5 \text{ (mg/mL)}}$$

7. The reconstituted sample should be translucent and homogeneous without visible particulates. If unsuspended powder is visible, the vial should be **gently** inverted again to ensure complete resuspension, prior to use.
8. Using a new, sterile 50-cc or 60-cc syringe, withdraw the reconstituted ABI-009 solution. Do not remove the rubber stopper from the ABI-009 vials as this can compromise the sterility of the drug preparation.
9. Inject the calculated dosing volume of reconstituted ABI-009 suspension into an empty sterile, standard PVC or non-PVC IV bag using an injection port. Inject perpendicularly into the center of the injection port to avoid dislodging plastic material into the IV bag. Repeat steps 9 and 10 until the patient's entire required dose is injected into the IV bag.
10. Remove the injection port.
11. Once the exact volume of reconstituted ABI-009 has been withdrawn from the vials, discard any excess solution left over in accordance with standard operating procedures for cytotoxic drugs.
12. Administer the calculated dosing volume of reconstituted ABI-009 suspension by IV infusion over 30 minutes (+/- 10 min). The use of in-line filters is not necessary; if used, in-line filters with pore sizes of < 15 microns (15 μ m) should not be used. Upon completion of infusion, the infusion catheter should be flushed with ~2 mL normal saline to ensure all drug has been infused.
13. Reconstituted ABI-009 suspension in IV bag should be used immediately, but may be stored for up to 4 hours at 2-8°C (36°- 46°F), followed by 4 hours at room temperature (<25°C).

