11. MONITORING, RECORDING AND REPORTING OF ADVERSE EVENTS

11.1. Toxicities of ABI-009

ABI-009 is a formulation of rapamycin. No unexpected toxicities not already known for rapamycin (Rapamune[®]) or the rapamycin prodrug, temsirolimus (Torisel[®]), were identified in the nonclinical toxicity studies, or observed in the phase 1 studies for ABI-009.

More details on the known precautions, warnings, and AEs of rapamycin and rapalogs are found in the Rapamune[®] and Torisel[®] Package Inserts [52, 53].

An AE is any noxious, unintended, or untoward medical occurrence that may appear or worsen in a patient during the course of a study. It may be a new intercurrent illness, a worsening concomitant illness, an injury, or any concomitant impairment of the patient's health, including laboratory test values (as specified by the criteria below), regardless of etiology. Any worsening (ie, any clinically significant adverse change in the frequency or intensity of a preexisting condition) should be considered an AE. A diagnosis or syndrome should be recorded on the AE page of the eCRF rather than the individual signs or symptoms of the diagnosis or syndrome. **Note:** Disease progression and death due will not be recorded as an AE.

Abuse, withdrawal, sensitivity or toxicity to the IP should be reported as an AE. Overdose, accidental or intentional, whether or not it is associated with an AE should be reported on the appropriate CRF, see [Section 7.2.3](#) for the definition of overdose. Any sequela of an accidental or intentional overdose of the IP should be reported as an AE on the AE CRF. If the sequela of an overdose is an SAE, then the sequela must be reported on an SAE report form and on the AE CRF. The overdose resulting in the SAE should be identified as the cause of the event on the SAE report form and CRF but should not be reported as an SAE itself.

All patients will be monitored for AEs during the study. Assessments may include monitoring of any or all of the following parameters: the patient's clinical symptoms, laboratory, pathological, radiological or surgical findings, physical examination findings, or other appropriate tests and procedures.

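### Section 7.2.3 counts any infusion faster than 30 minutes as an overdose, while Sections 7.1 and 8.3 permit 30 minutes +/- 10 min, so some permitted infusions are reportable as overdoses

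*Combined protocol and SAP*

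**What the plan says.** **Overdose definition.** Section 7.2.3 defines overdose in three ways: by dose, by frequency and by infusion rate. On the rate basis, "an overdose is defined as any rate faster than the protocol-specified rate of 30 minutes for each infusion". The dose-based definition has a 10% margin; the rate-based one has none.

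**Dosing instructions.** Section 7.1 specifies "IV infusion over 30 minutes, +/- 10 min". Section 8.3, step 12, tells staff to give the dose "by IV infusion over 30 minutes (+/- 10 min" with the bracket then closed.

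**Other mentions of infusion time.** The ECG-timing notes in Table 2 (footnote i) and in Sections 6.2.1 and 6.2.2 repeat the 10-minute window, but they are not dosing instructions. The synopsis (Study Treatments) gives 30 minutes with no window.

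**What follows from an overdose.** Section 11.1 refers to Section 7.2.3 for the definition and says: "Overdose, accidental or intentional, whether or not it is associated with an AE should be reported on the appropriate CRF". If a sequela is an SAE: "The overdose resulting in the SAE should be identified as the cause of the event on the SAE report form and CRF". That sentence goes on to say that the overdose should not be reported as an SAE in its own right.

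**The concern.** The same infusion can satisfy the dosing instruction and meet the overdose definition. This is an operative rule, because Section 11.1 relies on that definition to decide what is recorded and what is named as the cause of an SAE.

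What is at stake is the accuracy of the safety record. Applied literally, the text labels dosing that the protocol allows as overdose. If an SAE is then judged to be a sequela, the SAE form and CRF could attribute it to an overdose when the infusion was within the permitted window. The conflict starts just below the nominal 30 minutes, not only at the far edge of the window.

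**Working it through.** The plan states no figure to reproduce. The check compares two intervals of infusion time.

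**Inputs**
- Nominal infusion time: 30 minutes (Sections 7.1, 7.2.3 and 8.3).
- Permitted deviation: 10 minutes either way (Sections 7.1 and 8.3).
- Rate-based overdose: faster than 30 minutes, no tolerance (Section 7.2.3).

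For a given dose, a faster rate means a shorter infusion, so the overdose rule is read as a duration under 30 minutes.

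**Step 1: permitted durations.** 30 - 10 = 20 to 30 + 10 = 40 minutes, a width of 40 - 20 = 20 minutes.

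**Step 2: overdose durations.** Anything under 30 minutes.

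**Step 3: overlap.** From 20 to under 30 minutes, a width of 30 - 20 = 10 minutes. As a share of the permitted width, 10 / 20 = 0.5. This is half the width of the window, not half of infusions.

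| Infusion time | Permitted by 7.1 and 8.3? | Overdose by 7.2.3? |
|---|---|---|
| Under 20 min | No | Yes |
| 20 to under 30 min | Yes | Yes |
| 30 to 40 min | Yes | No |
| Over 40 min | No | No |

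Only the second row is contradictory. A 29-minute infusion falls in it just as a 20-minute one does.

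**Step 4: is the window exempted anywhere?** No. Section 7.2.3 mentions no window, Section 11.1 adds none, and the synopsis cannot settle the matter because it states 30 minutes alone.

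**Step 5: does it reach the analysis?**
- The primary endpoint (Section 10.5.2) and the sample size (Section 10.2) do not use infusion time.
- The exposure summaries in Section 10.5.4 use the number of doses, the average dose and the duration of treatment.
- Section 10.5.4 lists no overdose table, and none of its listed tables takes infusion time or overdose status as an input.

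**The case against.** The best defence is that the protocol-specified rate in Section 7.2.3 tacitly includes the window, because the operative dosing instructions specify 30 minutes with that window. The neighbouring frequency rule supports this: it calls anything more frequent than the required schedule an overdose without repeating the 2-day visit window of Section 7.2.1, and one would naturally read that window in. This makes misapplication less likely. It does not remove the conflict, since the rate-based rule names 30 minutes and covers any faster rate.

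A second defence is that little follows from the label. Section 11.1 uses should, not must, for both the CRF entry and the cause entry. The overdose is not itself an SAE, and a cause entry arises only once an SAE has been judged a sequela. Section 7.2 attaches no dose hold, reduction or discontinuation to an overdose. All of this stands, and it limits the point to safety reporting.

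A third is that some records could be checked later. Section 6.5 requires exact start and end times of infusion, but as part of the PK study, which samples only on Cycle 1 Days 1 and 8 and Cycle 2 Day 1. The documents do not show the same requirement for later doses.

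Two stronger readings are tempting and unsupported. A reader might infer that sites will classify these infusions differently; the CRF instructions are not in the documents, so this is not shown. A reader might also take the shorter permitted infusions to be an exposure or safety problem, since 20 minutes is 30 / 20 = 1.5 times as fast as 30. That ratio only restates the two durations, and nothing in the documents ties it to harm.

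**Conclusion.** The inconsistency holds as a matter of text: an infusion of 20 to under 30 minutes is both permitted and an overdose. It is confined to overdose records and any linked SAE cause entries.

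Its size is 10 of the 20 minutes of permitted width. How many infusions fall there cannot be derived, because the documents give no distribution of infusion times. The conclusion assumes only that faster than 30 minutes means a duration under 30 minutes for the assigned dose, and that Section 7.2.3 is read as written.

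It would go too far to say that the trial's results or its safety tables are compromised. ORR, the sample size and the planned safety tables are untouched. The point merits correction because it affects how safety events are recorded and attributed, and because correcting it is easy.

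**What to change.** Reconcile the rate-based definition in Section 7.2.3 with the dosing instructions in Sections 7.1 and 8.3 (step 12), so that no infusion the protocol permits is also a reportable overdose. Bring the synopsis, Table 2 footnote i, Sections 6.2.1 and 6.2.2 and the CRF guidance into line with the outcome. Which text governs is for the clinical team; this review takes no position on the infusion time.

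The cost is a one-sentence clarification, matching edits where infusion time is repeated, and matching CRF guidance. If issued as an amendment, it needs the investigator agreement and IRB approval set out in Section 13.4. No analysis, sample size or planned table has to change.
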